3.3.9 Meals during the Trial

There are no special requirements related to food and beverage intake during the trial. Patients should abstain from alcohol from day -2 to day 10 of the trial.

3.3.10 Blinding

The trial is open label. Neither patients, clinicians, trial staff nor pharmacists will be blind to the trial drug.

3.3.11 Previous / Concomitant Medication and Other Restrictions during the Trial

The use of acetaminophen (paracetamol) is allowed. Other medication to treat AEs may only be prescribed after consultation of the Sponsor unless there is an emergency that does not allow discussion. In the event medication is used, the name of the drug, the dose and dosage regimen will be recorded in the eCRF.

Strenuous activity (activity resulting in muscle pains or perspiration) is not allowed from day-2 to day 10 of the trial.

3.3.12 Treatment Compliance

To ensure treatment compliance, medication dosing will be supervised by the Principal Investigator or his/her deputy. The exact times of medication dosing will be recorded in the eCRF. The actual volume dosed will be checked.

3.3.13 Prohibited Medication During the Trial (including the screening period)

1. NSAIDs
2. Corticosteroids
3. Compounds intended to interfere with bone metabolism (e.g. Denosumab, Teriparatide, Romosozumab, Raloxifene).
4. Bisphosphonates
5. Supplements including Vitamin B6
6. Asfotase alfa

If there is a clinical indication to start any of these above medication, the subject should be withdrawn from the trial. Subjects who initiate any of the medication mention above during the trial period will be considered dropouts.

3.3.14 Female subjects

Women of Child Bearing Potential (i.e. fertile, following menarche and until becoming post-menopausal unless permanently sterile) must have adequate and effective contraception means. Methods that are considered as highly effective birth control methods are: 1) Combined (estrogen and progestogen containing) hormonal contraception associated with inhibition of ovulation (oral, intravaginal or transdermal), 2) progestogen-only hormonal contraception associated with inhibition of ovulation (oral, injectable, implantable), 3) intrauterine device (IUD), 4) intrauterine hormone-releasing system (IUS), 5) bilateral tubal occlusion, 6) vasectomised partner, 7) sexual abstinence. Contraception methods 3, 4, 5 and 6 have lower user dependency and should preferably be used, in particular when contraception is introduced as a result of participation in the clinical trial. (CTFG, 2020¹¹)

For post-menopausal female, with post-menopause defined as no menses for 12 months without an alternative medical cause, a high follicle stimulating hormone (FSH) level in the postmenopausal range may be used to confirm a post-menopausal state in women not using hormonal contraception or hormonal

replacement therapy. However, in the absence of 12 months of amenorrhea, a single FSH measurement is insufficient. (CTFG, 2020¹¹)

3.4 Sample collection

The Schedule of Assessments is presented in Table 1. All samples will be pseudonymized, collected and analyzed according to the instructions in the lab manual. Left over samples and samples for exploratory biomarkers will be bio-banked and stored at -80 °C in an appropriate facility. Unused samples will be retained for up to 10 years after completion of the trial and may be used for research purposes relating to HPP and/or the effects of ilofotase alfa on HPP disease parameters.

3.4.1 Primary endpoint samples

All samples to be obtained while fasting in the morning. There will be 3 samples obtained to determine baseline (day -2, day -1, and day 1 before randomization and dosing). There will be 12 samples obtained to determine changes in response to treatment (3 samples on day 1 (*2, 4, and 8 hours after start dosing*), and daily samples from day 2 until day 10.

3.4.1.1 PPi

All samples to be obtained while fasting in the morning and processed following the laboratory manual. Briefly, plasma samples will be centrifuged within 15 minutes of collection to yield platelet-depleted plasma, after which they will be stored at -80 °C until assessment according to the kit manufacturer instructions.

3.4.1.2 PLP

All samples to be obtained while fasting in the morning and processed following the laboratory manual. Briefly, all blood samples to be obtained while fasting in the morning, plasma samples will be centrifuged within 15 minutes of collection to yield platelet-depleted plasma, after which they will be stored at -80 °C until assessment according to the kit manufacturer instructions.

3.4.2 Exploratory assessments

Immediately consecutive sampling (second morning urine) of urine and blood for creatinine, phosphorus, and calcium concentrations to assess phosphate reabsorption (TmP/GFR and TRP) kidney function and Ca/creatinine ratio.

Blood samples for: 25 OH Vitamin D, ALP activity and Isoenzymes, iFGF-23, PTH, CTX, PINP, Osteocalcin, PL, and processed following the laboratory manual.

Blood sample for purine measurement processed following the laboratory manual.

For serum collection, blood samples will be allowed to clot for 30-60 minutes and then centrifuged for 15 min to separate the serum. For plasma sample collection, blood samples will be centrifuged within 15 minutes of collection to yield plasma. After collection of the serum/plasma in new tubes the samples will be stored at -80 °C until assessment.

Urine samples (for PEA, absolute and relative to Creatinine) will be collected as fresh as possible and transferred specimen from standard urine collection cup into the pre- labeled transfer tubes. After collection the urine samples will be stored at -80 °C until assessment.

3.5 Pharmacokinetic and Safety Variables

The Schedule of Assessments is presented in Table 1.

3.5.1 Pharmacokinetic Measurements

3.5.1.1 Ilofotase alfa concentration

Blood samples of 3 mL will be collected via an indwelling iv catheter or by a direct venipuncture at the time points indicated in Table 3 (see also Schedule of Assessments presented in Table 1).

The time clock (zero hours) starts at commencement of the iv dose of ilofotase alfa. The 60 minutes, 2-, 4- and 8-hours post dose blood samples may be collected within ±5 minutes of the scheduled times,

within ± 60 minutes for all the other scheduled times. The exact times of blood sampling will be recorded in the eCRF.

Table 3. PK sample schedule for determination of ilofotase alfa

Pre-dose	day 1	Pre-dose (2 samples)
Post infusion	day 1	60 min (immediately post dose) 2h 4h 8 h
	day 2	24 h
	day 3	48 h
	day 4	72 h
	day 5	96 h
	day 6	120 h
	day 7	144h
	day 8	168 h
	day 9	192 h
	day 10	216 h

Note: The 60 minutes sample is to be taken from the arm NOT used for infusion.

PK samples will be analyzed by a central laboratory. Processing, storage, and shipment of the samples are described in detail in the Laboratory Manual.

3.5.2

Safety and Tolerability Measurements

Safety and tolerability assessments will consist of AEs, and results of vital signs, clinical laboratory tests, physical examinations, and anti-drug antibodies (ADA). Assessments will be performed in accordance with the schedule of assessments. The actual times of all assessments will be recorded in the eCRF.

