⁶ PK sampling on day 1 will include baseline, end of infusion, 2, 4 and 8 hours post infusion

⁷ Samples to be drawn in the morning while fasting, for PPi and PLP (both Vitamers)

⁸ Samples at baseline, 2, 4 and 8 hours after start dosing will be in non-fasted patients

⁹ Immediately consecutive sampling (second morning urine) of urine and blood for PEA, creatinine, phosphorus, and calcium concentrations. To assess phosphate reabsorption (TmP/GFR and TRP) kidney function and Ca/creatinine ratio

¹⁰ 25 OH Vitamin D, ALP Isoenzyme, c-Terminal iFGF-23, PTH, CTX, PINP, Osteocalcin, PEA Urine (absolute und relative to sCreat), Purines and other biomarkers

¹¹ This includes SAE reporting

¹⁰ Baseline is defined as measurements taken on day -2, day -1 and day 1. Measurements taken on day 1 must be taken at any time up to immediately before randomization to be considered as baseline measurements. Measurements taken at or after randomization are not considered baseline measurements. Note that there is no day 0.

TABLE OF CONTENTS

1. INTRODUCTION	12
1.1 Background	12
1.1.1 Alkaline Phosphatase and Hypophosphatasia	12
1.1.2 Recombinant Human Alkaline Phosphatase (ilofotase alfa)	12
1.1.3 Clinical Studies with Recombinant Human Alkaline Phosphatase (ilofotase alfa)	12
1.2 Rationale.....	12
Risk - Benefit	13
2. OBJECTIVES	13
3. INVESTIGATIONAL PLAN.....	13
3.1 Trial Design and Plan.....	13
3.1.1 Trial design.....	13
3.1.2 Screening and Informed consent.....	13
3.1.3 Treatment Period.....	13
3.1.4 Follow-up	13
3.1.5 Discussion Trial Design.....	13
3.2 Selection of Trial Population.....	14
3.2.1 Inclusion Criteria	14
3.2.2 Exclusion Criteria	14
3.2.3 Removal of Patients from Therapy or Assessment.....	15
3.3 Treatments.....	15
3.3.1 Treatments Administered	15
3.3.2 Identity of Investigational Product	15
3.3.3 Trial Drug Preparation	15
3.3.4 Trial Drug Administration.....	16
3.3.5 Trial Drug Handling and Storage	16
3.3.6 Drug accountability.....	16
3.3.7 Drug Storage	16
3.3.8 Method of Assigning Patients to Treatment Groups	16
3.3.9 Meals during the Trial	17
3.3.10 Blinding	17
3.3.11 Previous / Concomitant Medication and Other Restrictions during the Trial	17
3.3.12 Treatment Compliance	17
3.3.13 Prohibited Medication During the Trial (including the screening period)	17
3.3.14 Female subjects	17
3.4 Sample collection.....	18
3.4.1 Primary endpoint samples	18
3.4.1.1 PPi.....	18
3.4.1.2 PLP.....	18
3.4.2 Exploratory assessments	18

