3.3.4 Trial Drug Administration

Only patients enrolled and randomized in the trial may receive trial drug. Start and stop time and date of each trial drug administration will be collected in the electronic case report form (eCRF). Trial drug is administered as an iv infusion using an infusion line with an in-line filter and dosing syringe. Infusion will take place at a constant rate of 50 mL/hour for 60 minutes.

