3.5.3 Total of Blood Volume

Table 4 presents the number and volume of blood samples and the total volume of blood that will be collected throughout the trial per patient and trial part.

Table 4. Number and Volume of Blood Samples and Total Blood Volume Collected per Patient

Assessment	Maximum # samples	mL of blood per sample	Total volume of blood (mL)
Clinical laboratory	3	8	24
Clinical Chemistry			
Hematology			
ADA	2	4	8
Pharmacokinetics	15	3	45
ilofotase alfa			
Pharmacodynamics	15	14	210
Total volume of blood drawn			287

3.5.4

Timing of Assessments

The actual times of all assessments will be recorded in the eCRF.

For PK blood sampling, post dose blood samples may be collected within ± 5 minutes of the scheduled time for samples the first 8 hours post dose, within ± 60 minutes of the scheduled time for all other samples.

For safety assessments, pre-dose assessments on day 1 will also be performed between waking up and dosing. Sampling for clinical laboratory assessments at screening and post-dose at day 10 does not have a time-window.

In the event assessments are planned for the same scheme time, the order of the assessments should be arranged in such a way that PK blood sampling is done exactly on time, in practice generally vital signs will be done first, followed by blood sampling (exactly on time), followed by safety laboratory sampling. Baseline is defined as measurements taken on day -2, day -1 and day 1. Measurements taken on day 1 must be taken at any time up to immediately before randomization to be considered as baseline measurements. Measurements taken at or after randomization are not considered baseline measurements.

3.6

Statistical Procedures

3.6.1

Trial Populations

Intention to Treat population (ITT)

All randomized patients will be included in the ITT population.

Population for the safety analysis (SAS)

All patients who have received trial medication.

Population for the PK analyses (PKS)

All patients who have received ilofotase alfa and for whom sufficient bioanalytical data are available to calculate reliable estimates of the PK parameters.

3.6.2

Statistical Evaluations

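### The ±5 minute window on the 60-minute PK sample admits draws before the infusion ends, so the near-peak concentration can be understated

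*Protocol*

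**What the plan says.** Four statements in the protocol bear on this sample.

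- **Time origin (Section 3.5.1.1):** "The time clock (zero hours) starts at commencement of the iv dose of ilofotase alfa".
- **Infusion length (Section 3.3.4):** "Infusion will take place at a constant rate of 50 mL/hour for 60 minutes".
- **Window (Section 3.5.1.1):** "The 60 minutes, 2-, 4- and 8-hours post dose blood samples may be collected within ±5 minutes of the scheduled times". Section 3.5.4 repeats it: "post dose blood samples may be collected within ± 5 minutes of the scheduled time for samples the first 8 hours post dose".
- **What the sample is meant to be:** Table 3 lists it among the times after the infusion as "60 min (immediately post dose". Table 1 footnote 6 reads "PK sampling on day 1 will include baseline, end of infusion, 2, 4 and 8 hours post infusion".

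The sample is taken from the arm that does not carry the infusion. Sampling times (Section 3.5.1.1) and infusion start and stop times (Section 3.3.4) go into the eCRF. Section 3.6.2.3 plans concentration-time plots by treatment, including geometric means, with listings and descriptive statistics. It places PK parameters outside the Clinical Trial Report.

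**The concern.** Under a constant-rate infusion the concentration rises until the infusion stops. The 60-minute sample is the only one scheduled near that peak, because the next is at 2 h. A window centred on the planned stop lets staff draw the sample while drug is still running and remain within the stated tolerance, although both labels describe a sample taken once the infusion has ended. The sample is also fixed to nominal clock time, so it does not move with the actual stop if the infusion runs over.

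The PK profile is an exploratory objective, and each arm has at most six patients. At stake is whether the near-peak value in the listings, plots and geometric means is what its label says.

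A related inconsistency concerns the later day 1 samples. Footnote 6 counts 2, 4 and 8 h from the end of infusion, whereas Section 3.5.1.1 counts from the start.

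**Working it through.** **Inputs from the protocol.** Volume 50 mL (Section 3.3.3); rate 50 mL/h (Section 3.3.4); clock zero at infusion start and tolerance ±5 minutes (Section 3.5.1.1).

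**Input assumed.** The protocol gives no elimination half-life, so a range is shown. The model is one-compartment with a constant-rate infusion.

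**Step 1: the plan's own figure.** Duration = 50 mL ÷ 50 mL/h = 1 h = 60 minutes, as stated. Window = 60 ± 5 = 55 to 65 minutes. At minute 55 the volume given is 50 × 55/60 = 45.8 mL, or 91.7% of the dose.

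**Step 2: an on-time infusion.** With k = ln 2 / half-life and t in minutes, C(t) is proportional to 1 − exp(−kt) up to 60 minutes, and C(t) = C(60) × exp(−k(t − 60)) afterwards. Hence

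- early draw: C(55)/C(60) = (1 − exp(−55k)) / (1 − exp(−60k));
- late draw: C(65)/C(60) = exp(−5k).

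| Assumed half-life | Shortfall at 55 min | Shortfall at 65 min |
|---|---|---|
| 10 min | 0.7% | 29.3% |
| 30 min | 4.1% | 10.9% |
| 1 h | 5.9% | 5.6% |
| 4 h | 7.7% | 1.4% |
| 24 h | 8.2% | 0.2% |
| no elimination | 8.3% | 0% |

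The early-side ceiling is 1 − 55/60 = 8.3%. The two sides are equal at a half-life of about 57 minutes. A draw at minute 60 has no shortfall.

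**Step 3: an overrun.** If the infusion ends after minute 65, every draw within the window falls during the infusion. For an illustrative 70-minute infusion at constant rate, C(60)/C(70) = (1 − exp(−60k)) / (1 − exp(−70k)). This is 0.902 at a half-life of 1 h, 0.867 at 5 h and 0.859 at 24 h, so a 60-minute draw is about 10% to 14% below the end-of-infusion value.

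**Step 4: effect on an arm's geometric mean.** If one of six patients is drawn at minute 55, the geometric mean is multiplied by at least 0.917^(1/6) = 0.986, a fall of at most 1.4%. If all six are, the fall is at most 8.3%.

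**Step 5: with a window of 0 to +5 minutes after the actual stop.** The early-side column and the overrun error disappear, and the late-side column stays. For an on-time infusion, the worst case changes from the larger of the two columns to the late-side one. It therefore never gets worse, and it improves only if the half-life exceeds about 57 minutes.

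**Step 6: time origin.** Two hours after the start is 1 h after the end of a 60-minute infusion. The two readings of the 2, 4 and 8 h samples differ by 60 minutes, which is 60/5 = 12 times the tolerance.

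**The case against.** The strongest reply is that the labels already settle the matter. Staff told to draw an end-of-infusion sample will not draw it while the pump is visibly running, Section 3.5.4 asks for PK sampling to be exactly on time, and Section 3.3.12 has dosing supervised. This makes early draws less likely. It does not remove the conflict, because the tolerance is explicit and nothing gives the labels priority over it. The overrun case is hypothetical, since the protocol plans exactly 60 minutes.

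Several other objections stand and limit the point:

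- PK is exploratory and no peak-concentration endpoint is named.
- Because sampling and infusion times are recorded, a sample drawn during the infusion can be identified and is valid input to a model-based analysis such as the possible population PK work. What remains is the effect on listings, plots and descriptive summaries.
- Late draws also miss the peak. At a 0.5 h half-life the late loss (10.9%) exceeds the largest possible early loss (8.3%), and the fix leaves it in place.

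A reader might infer two stronger things that the documents do not support. One is that the peak is understated as a rule, or that the dose comparison is biased. An on-time draw at minute 60 loses nothing, and the same rule applies to both arms. The other is that the wider allowance, "within ± 60 minutes for all the other scheduled times", would let a pre-dose sample be drawn after the start. Section 3.5.4 states the allowances for post-dose samples, and Table 3 gives the pre-dose samples no clock time to which ±60 minutes could attach.

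**Conclusion.** The point holds as a small one. The stated window accepts a draw up to 5 minutes before the infusion ends, or wholly during it after an overrun of more than 5 minutes. This conflicts with the labels in Table 3 and Table 1 footnote 6. The near-peak concentration can therefore be understated. For an on-time infusion the loss in one patient's value is about 4% to 8% at half-lives of 0.5 h or more and never above 8.3%. These sizes rest on the one-compartment model and the assumed half-lives. The conflict between window and labels, and the one-hour difference in time origin, rest on the text alone. The primary PPi and PLP endpoint is unaffected.

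**What to change.** In Section 3.5.1.1, Table 3 and Section 3.5.4, define this sample as taken 0 to +5 minutes after the recorded end of infusion, and remove it from the ±5 minute rule. In the same edit, give the 2, 4 and 8 h PK samples one time origin in Table 1 footnote 6, Table 3 and Section 3.5.1.1. Section 3.4.1 times the day 1 PPi and PLP samples from the start of dosing, so the same origin would keep the PK and biomarker samples aligned. The ±5 minutes can stay for the 2, 4 and 8 h samples. The pre-dose samples need no change.

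The cost is one line in each place. No extra sample, blood volume, staff or data field is needed, because the stop time is already collected. The limitation is that the late-side loss remains, and for an on-time infusion the worst case improves only at half-lives above about 57 minutes. At any half-life the sample would match its label and follow an overrun.

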3.5.2.1 Adverse Events

An AE is defined as any untoward medical occurrence in a patient administered a trial drug and which does not necessarily have a causal relationship with this treatment. An AE can therefore be any unfavorable and unintended sign (including an abnormal laboratory finding), symptom, or disease temporally associated with the use of a trial drug, whether related to the trial drug.

At several time points before and after drug administration, patients will be asked non-leading questions to determine the occurrence of AEs. Patients will be asked in general terms about any AEs at regular intervals during the trial period. In addition, all AEs reported spontaneously during the trial will be recorded.

All answers will be interpreted by the Principal Investigator using the Medical Dictionary for Regulatory Activities (MedDRA), an internal validated medication dictionary for AEs and will be recorded in the AEs Record. Details on the rating of the intensity of the (S)AEs and relationship to the trial treatment are given in Appendix 7.1.

3.5.2.2 Vital Signs

During the trial, blood pressure and pulse will be recorded after 5 minutes of rest in the supine position and after 2 minutes of rest in the standing position. These assessments will be made using an automated device. Body temperature and respiratory rate will be measured subsequently or at the same time as blood pressure and pulse.

3.5.2.3 Electrocardiogram

At screening a standard 12 lead ECG will be recorded after 5 minutes of rest in the supine position using an ECG machine. The following ECG parameters will be recorded: heart rate, PR-interval, QRS-duration,

QT-interval, and QTc-interval (Fridericia's formula) together with the Principal Investigator's conclusion on the ECG profile. This ECG will serve as reference in case additional ECG are made on clinical indication.

3.5.2.4 Physical Examination

Physical examination will be performed according to the procedures of the trial center.

3.5.2.5 Anti-Drug Antibodies (ADA)

Blood samples of 4 mL will be taken at baseline (day 1) and at the end of the observation period (day 10) to determine the presence of antibodies against ilofotase alfa. The date and time of blood collection will be documented in the eCRF.

Immunological testing will be performed by a central laboratory by using an Enzyme Linked Immunosorbent Assay (ELISA) on a Meso Scale Discovery (MSD) platform. The assay is validated in human and septic serum samples. Processing, storage, and shipment of the samples are described in detail in the Laboratory Manual.

3.5.2.6 Clinical Safety Laboratory

Blood samples for clinical laboratory assessments will be collected at screening, day 1, and day 10, and analyzed locally according to the procedures of the trial center.

The following parameters will be measured:

Clinical chemistry (serum quantitatively):

total bilirubin, gamma glutamyl transferase (gamma-GT), aspartate aminotransferase (AST) (serum glutamic-oxaloacetic transaminase [SGOT]), alanine aminotransferase (ALT) (serum glutamic-pyruvic transaminase [SGPT]), lactate dehydrogenase (LDH), creatinine, blood urea, total protein (albumin and total), inorganic phosphate, sodium, potassium, calcium, glucose.

Hematology (blood quantitatively):

leucocytes, erythrocytes, hemoglobin, hematocrit, thrombocytes, partial automated differentiation: lymphocytes, monocytes, eosinophils, basophils, neutrophils, mean corpuscular volume (MCV), mean corpuscular hemoglobin (MCH), mean corpuscular hemoglobin concentration (MCHC).

Urinalysis (urine qualitatively):

hemoglobin, urobilinogen, ketones, glucose, protein.

In the event of unexplained or unexpected clinical laboratory test values, the test(s) will be repeated as soon as possible and followed up until the results have returned to the normal range and/or an adequate explanation for the abnormality is found. The clinical laboratory will clearly mark all laboratory test values that are outside the normal range and the Principal Investigator will indicate which of these deviations are clinically significant. These clinically significant deviating laboratory results will then be recorded as AEs and the relationship to the treatment will be indicated (see also Appendix 7.1).

